5.7 Definition of Visit Windows

All data should be presented by nominal visit date and name as recorded on the eCRF (in chronological order). Visits will not be reassigned from the recorded nominal visit to any other visit based on dates.

5.8 Changes from the Planned Statistical Analysis in Protocol

The Clinical Study Protocol states that the correlations between average coagulation parameters (TGA parameters: lag time, time to peak thrombin generation, peak thrombin generation, ETP and FVIII trough levels) and ABR will be assessed/displayed by boxplots. For consistency with the presentation in the 261302 continuation study, linear regression plots with 95% CIs will be used instead.

The Clinical Study Protocol states that IR at 15-30 minutes post-infusion will be calculated based on FVIII activity at baseline and steady-state. Instead, IR at C_{max} will be determined for PK assessment visits. Incremental recovery over time at scheduled IR visits will be preseted for IR at 15-30 minutes post-infusion.

In addition to the analysis described in the protocol, a listing and corresponding summary table of IR resulting from the use of 3 000 IU vials will be presented. The table will only contain descriptive statistics of IR at 15-30 minutes post-infusion by scheduled visit.

5.9 Statistical Tests

The default significance level will be 5%; CIs will be 95% and all tests should be two-sided, unless otherwise specified in the description of the particular analysis.

P-values obtained from statistical inference tests should be presented using four decimal places.

Unless otherwise specified the default summary statistics for quantitative variables will be as follows:

- The number of subjects in each category (n).
- Mean.
- Standard deviation (SD).
- First quartile (Q1).
- Median.
- Third quartile (Q3).
- Inter-quartile range (IQR); calculated as $Q3 - Q1$.
- Minimum.
- Maximum.

The number of subjects (n) with missing or unavailable results for quantitative variables will be presented as “Not reported” where applicable. A “Not reported” category should only be presented should there be unavailable results. No distinction based on the reason for unavailable results will be made within any presentations.

If the original data has N decimal places (as derived from the raw data) (i.e., decimal precision [N]), then the summary statistics are to contain the following decimal places (with a maximum of three decimals):

- Minimum and maximum: N.
- Mean, median, Q1, Q3 and IQR: N + 1.
- SD and CI: N + 2.

For qualitative variables the number (n) and percentage (%) of subjects in each category will be the default summary presentation. Unless otherwise specified, percentages should be calculated relative to the total number of subjects in the relevant analysis set and treatment arm as described in the latest version of the Output Templates. For unavailable assessments a “Not reported” category should be presented. A “Not reported” category will only be presented if applicable. The “Not reported” category should be presented with a percentage so that the sum of the percentages of all categories, including the “Not reported” category, totals 100%. No distinction based on the reason for unavailable results will be made in any presentations.

All values should be rounded using the SAS[®] function ROUND. All calculated percentages should be presented using one decimal place.

The following data handling will be applied for PK assessments/analysis.

All PK concentrations/FVIII activity levels will be reported and analyzed with the same precision as the source data provided by the bioanalytical laboratory regardless of the amount of significant figures or decimals the data carry. Derived pre-infusion-corrected concentrations will be rounded to the same decimal precision as the source data for presentations in listings and calculation of descriptive statistics. Unrounded derived PK data will be considered the source data for the calculation of descriptive statistics and the statistical analysis. For most derived PK parameters, three significant digits will be used as the standard rounding procedure, with the following exceptions:

- Parameters directly derived from source data (eg, C_{\max}) will be reported and analyzed with the same precision as the source data.
- Parameters derived from actual elapsed sample collection times (eg, T_{\max}) are to be reported with the same precision as the actual elapsed sampling time value of the source data.

For the reporting of descriptive statistics for PK data, the mean, geometric mean, median, Q1, Q3, IQR, SD, and CIs are to be presented to 1 digit more precision. The minimum and maximum are to be presented to the same precision. Coefficient of variation (CV%) and geometric CV% are always to be reported to 1 decimal place.

5.10 Common Calculations

For quantitative measurements, change from baseline is calculated as:

Change from Baseline at Visit X = Test Value at Visit X – Baseline Value

Change from pre-infusion is calculated as:

Change from pre-infusion at Visit X = Test Value at Visit X post-infusion – Test Value at Visit X pre-infusion

5.11 Multicenter Studies

This study is conducted by multiple Investigators at multiple centers internationally.

Unless specified otherwise, all summaries should be produced overall and will not be summarized by center as the number of subjects per study site is too small.

5.12 Examination of Subgroups

The following subgroups will be utilized in analyses as indicated in the latest version of the Output Templates as well as the various sections to follow:

- Stratum, as derived from the pre-study ABR and pre-study treatment type, captured on the Hemophilia A Treatment History eCRF panel:
 - Pre-study prophylaxis treatment with $ABR < 5$.
 - Pre-study prophylaxis treatment with $ABR \geq 5$.
 - Pre-study on-demand treatment.

- Age groups (years) (per different regulatory standards, resulting in overlapping groups), using age at informed consent as obtained from the Demographics eCRF panel:
 - European Medicines Agency (EMA):
 - European (EU) Age Group ≥ 12 to < 18 .
 - EU Age Group ≥ 18 .
 - Food and Drug Administration (FDA):
 - United States (US) Age Group ≥ 12 to < 17 .
 - US Age Group ≥ 17 .
- Race as obtained from the Demographics eCRF panel:
 - Asian.
 - Black or African American.
 - Native Hawaiian or other Pacific Islander.
 - White.
 - Other.

5.13 Categorization of Outcome Variables

The following categorization of outcome variables will be used in the analyses as indicated in the latest version of the Output Templates and in the following sections as applicable. Definitions for the below categories are provide in Section 7.1.2: Bleeding Episodes:

- Geographical location:
 - US.
 - Europe.
 - Asia Pacific (APAC).
- Bleed type as obtained from the Bleeding Episodes eCRF panels:
 - Spontaneous/Unknown Bleeds.
 - Injury related bleeds.
- Bleed severity as obtained from the Bleeding Episodes eCRF panels:
 - Bleeds of minor severity.
 - Bleeds of moderate severity.
 - Bleeds of major severity.
- Bleed location as obtained from the Bleeding Episodes eCRF panels:
 - Joint bleeds.
 - Non-joint bleeds.

- Bleed timing as derived using the bleed dates from the Bleeding Episodes eCRF panels:
 - Weekday bleeds.
 - Weekend bleeds.
- Also:
 - Morning bleeds.
 - Afternoon bleeds.
 - Evening bleeds.
- Number of bleeds during the study as obtained from the Bleeding Episodes eCRF panels:
 - No bleeds during the study.
 - At least one bleed during the study.

5.14 Multiple Comparisons/Multiplicity

Not applicable.

6. STUDY SUBJECTS

6.1 Disposition of Subjects

All subjects with informed consent provided will be accounted for in this study.

Each subject is to participate in the study for approximately a year or until premature study discontinuation. A completion/follow-up assessment will be performed for each subject at study exit.

Subject listings will be presented on the following disposition related items using the ENR:

- Subjects transitioning from other BAX 855 studies.
- Subject disposition in general.
- Informed consent with inclusion/exclusion criterion exceptions.
- Protocol deviations.
- Visit dates.
- Analysis sets.

Summary tables will be presented on subject disposition, protocol deviations and analysis sets using the ENR.

The following information items are obtained from the eCRF:

- Informed consent and protocol version under which the subject enrolls onto the study (Informed Consent eCRF panel):
- Inclusion and exclusion criteria met and/or not met (Inclusion/Exclusion Criteria [transitioning subjects] and Inclusion/Exclusion Criteria [New subjects]) eCRF panels).
- Visit dates (Date of Visit eCRF panel).
- Other studies in the BAX 855 program the subject participated in (Demographics eCRF panel).
- Study completion (Completion/Termination eCRF panel):
- AE term and number (Adverse Event eCRF panel).
- Treatment arm assignment including date randomized (Randomization eCRF panel).
- Study medication administrations in the PROPEL study (Study Infusion eCRF panel).

The following derivations will be made based on the eCRF reported results:

- A subject is considered to be enrolled if date of informed consent is present.
- A subject is considered screening failure if they present with a disposition record of Screening failure as recorded on the end of study eCRF.
- A subject is considered to have received PK dose if recorded as such on the infusion for PK assessment eCRF.
- A subject is considered randomized if assigned to one of the two treatment arms as recorded on the Randomization eCRF.
- A subject is considered to have been dosed prophylactically if any study medication administration or part thereof, occurred for the subject with reason of ‘prophylaxis’ as recorded on the infusion eCRF pages or within the subject diary.
- A subject is considered to be completed if the reason for termination indicates the subject completed the study. Otherwise the subject should be considered discontinued. For the first 6-month period, a subject is considered to be completed if not discontinued before or on ObsDay 182. For the second 6-month period, the subject needs to have a disposition or bleed record at or after ObsDay 364.

6.1.1 Protocol Deviations

Protocol deviations should be summarized by age group, site and classification (critical, major or minor) presenting the number of deviations per site and the number of subjects having the particular deviation.

The information on protocol deviations is obtained from the IQVIA CTMS and/or as identified in the data review meeting to be held for determination of the PPAS and PKAS.

Protocol deviations from the CTMS will be coded to standardized categories and provided as part of the CTMS transfer to Biostatistics.

Changes to the procedures or events, which may impact the quality of the PK data, will be considered significant protocol deviations/events and will be described within the clinical study report body text. These changes or events are to include any circumstances that alter the evaluation of the PK. Examples of protocol deviations that are important for PK are provided below. Actions to be taken on some of these are discussed further in Section 9: Evaluation of Pharmacokinetics.

- Sample processing errors that lead to inaccurate bioanalytical results.
- Inaccurate dosing on the day of PK sampling due to administration incidences or lack of compliance to the protocol.
- Dosing time (start and/or stop time of infusion) not available.
- Blood sampling date and time not available.
- Missing PK samples at important phases of the PK profile.
- Inadequate washout period prior to IP administration.
- Interruption of infusion.

Affected data will be evaluated by the pharmacokineticist to determine whether or not they can be included in the PK analysis. Subjects and/or data with important deviations or other data issues that are not included in the PKAS should be reported in listings, along with the reason for exclusion. Other changes to the procedures or events which do not impact the quality of the PK data will not be considered significant protocol deviations for PK analysis. A common example of a non-significant protocol deviation is a deviation from blood collection times.

6.2 Demographic and Baseline Characteristics

Subject listings are planned for the following items using the analysis set indicated:

- Baseline demographics (SAS).
- Previous participation in PROPEL or Baxter/Baxalta studies (ENR).
- Haemophilia A history and blood group information (SAS).
- Target joint specification at screening (SAS).

Summary tables are planned for baseline demographic and characteristics as well as disease and subject characteristics using the SAS, FAS, PPAS and PKAS:

Demographic and baseline characteristics summaries should be presented by (see Section 5.12: Examination of Subgroups):

- Age group.

The following information items are obtained from the eCRF:

- Demographics and previous PROPEL and/or Baxter/Baxalta study participation (Demographics eCRF panel).
- Height and weight at Screening (Vital Signs eCRF panels).
- Information on haemophilia A history, blood group, family history and target joint identification at Screening (Haemophilia A History/Blood Group/Target Joint Identification eCRF panel).

The following information is obtained from the Medical team based on medical histories reported in the *Medical History* eCRF panels:

- Whether a specific medical history can be considered as haemophilia arthropathy.
- Categorization of gene mutation for use in summaries.

The following information is obtained from the central laboratory:

- Hepatitis C virus antibody at Screening.
- Human Immunodeficiency Virus (HIV) results at Screening.

The following derivations will be made based of the eCRF reported results:

- Age at informed consent (years) is calculated as:

$$\text{Age at Screening (years)} = \text{Year of Reference Start Date} - \text{Year of Birth}$$

- Body mass index (BMI) is derived as:

$$\text{BMI}(kg/m^2) = \text{Weight}(kg) / \left[\frac{\text{Height}(cm)}{100} \right]^2$$

- Race will be presented as “Mixed” in summaries if more than one race is selected on the Demographics eCRF panel.
- The number of target joints at Screening will be counted from the eCRF.
- Average ABR based on previous twelve months will be categorized as:
 - <1.
 - 1 to <3.
 - 3 to <5.
 - 5 to <7.
 - 7 to <10.
 - 10 to <20.
 - 20 to <30.
 - 30 to <40.
 - 40 to <50.
 - 50 to <60.
 - ≥60.

A condensed categorization of ABR based on the previous twelve months, corresponding to the stratification of subject will be made as follows:

- ≤5.
- >5.

The presence of haemophilia arthropathy should be determined as present if any medical history is present that can be considered as haemophilia arthropathy, otherwise should be determined as absent.

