4.2 Safety Analysis Set (SAS)

The safety analysis set (SAS) is to comprise all subjects in the ENR with at least one BAX 855 infusion. All safety analyses will be performed on the SAS.

Information on dosing with BAX 855 is obtained from the following eCRF panels:

- *Study Infusion (both ERT Integration and Missed and on site infusions).*
- *Infusion for Determination of Incremental Recovery.*
- *Infusion for PK Assessment.*

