5.3 Reference Start Date, Surgery Day and Observation Days

5.3.1 Reference Start Date

Reference start date is defined as the day of the subject's first BAX 855 PK-guided prophylactic infusion, after enrolment in the 261303 protocol (henceforth referred to as the PROPEL study) and will be referred to as ObsDay 1. Subjects who discontinue study participation prior to receiving any BAX 855 prophylactic administration in the PROPEL study are not to have a reference start date.

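### SAP 6.2 computes age at informed consent from the year of first prophylaxis, contradicting its own label and SAP 5.12; if the formula feeds the age groups, some safety subjects have no age and some adolescents become adults

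*SAP*

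**What the plan says.** SAP 6.2 lists, among the derivations made from eCRF data, one introduced by "Age at informed consent (years) is calculated as". The formula beneath it names its result as age at screening and sets it equal to "Year of Reference Start Date" minus year of birth. No month or day enters.

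SAP 5.3.1 fixes the anchor: "Reference start date is defined as the day of the subject's first BAX 855 PK-guided prophylactic infusion". It adds that subjects who discontinue before any prophylactic administration "are not to have a reference start date".

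SAP 5.12 defines the EMA groups (12 to <18, and 18 or over) and the FDA groups (12 to <17, and 17 or over) "using age at informed consent as obtained from the Demographics eCRF panel". SAP 6.2 refers back to 5.12 for age group.

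On the safety population, SAP 4.2 states: "The safety analysis set (SAS) is to comprise all subjects in the ENR with at least one BAX 855 infusion". The PK-assessment infusion is one of the listed sources of dosing information, and SAP 8.1 treats that infusion as first administration for safety purposes. Adverse event, laboratory, immunogenicity and vital-sign tables (SAP 8.1 to 8.4) are all presented by age group.

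**The concern.** One variable carries three time anchors (consent, screening, first prophylaxis) and two possible sources (a computed value in 6.2, an eCRF panel in 5.12). Section 6.2 is the only place that states a computation, so a programmer could reasonably apply it wherever age at consent is called for.

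Two things would then go wrong. Subjects who belong to the safety population but have no Reference Start Date would get a missing age, in a plan whose main safety tables are split by age. And differencing calendar years, with the later year taken from first prophylaxis, can only push age up. Subjects just under the 17 or 18 cut-off would move from the adolescent to the adult group. Those groups exist to serve regulatory requirements, and the adolescent groups may be small.

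**Working it through.** The plan gives no figure to reproduce; this is a check of a derivation rule.

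**Missing age.** A subject who consents, receives the PK infusion and leaves before prophylaxis is in the Safety Analysis Set (SAP 4.2), has no Reference Start Date (SAP 5.3.1), and so has no value from the 6.2 formula. The same follows for a transitioning subject who takes study product under the previous regimen from screening (Protocol 10.3.1) and leaves before the first PK-guided dose. Age at the consent date is always definable, because this set is a subset of the enrolled set, which requires signed consent (SAP 4.1).

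**Upward bias: inputs.**
- Planned lag from consent to first prophylaxis: about 6 weeks of screening plus 6-8 weeks for PK, dose calculation and randomization (Protocol synopsis), which is 12-14 weeks or 84-98 days.
- Nominal maximum: 56 days for screening (Protocol 10.3) plus 56 days from PK assessment to baseline (Protocol 21.2), which is 112 days.
- Assumptions: consent date and birthday uniform over the year; ages uniform within the adolescent group.

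**Formulae.** Let *f* be the lag divided by 365.25. The formula exceeds completed years at consent by 1 if the birthday falls later in the consent year, and by a further 1 if the lag crosses 31 December. Then:
- P(no excess) = (1−f)²/2
- P(excess of at least 1) = 1 − (1−f)²/2, the share of true 17-year-olds put at 18 or over
- P(excess of 2) = f²/2, the share of true 16-year-olds put at 18 or over
- The last two sum to 0.5 + f, so the share misplaced is (0.5+f)/6 over ages 12 to <18 and (0.5+f)/5 over ages 12 to <17.

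| Lag (days) | f | No excess | Excess ≥1 | Excess 2 | Share of 12 to <18 | Share of 12 to <17 |
|---|---|---|---|---|---|---|
| 0 | 0 | 50.0% | 50.0% | 0% | 8.3% | 10.0% |
| 84 | 0.230 | 29.6% | 70.4% | 2.6% | 12.2% | 14.6% |
| 98 | 0.268 | 26.8% | 73.2% | 3.6% | 12.8% | 15.4% |
| 112 | 0.307 | 24.0% | 76.0% | 4.7% | 13.4% | 16.1% |

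A simulation of 1,000,000 draws agrees to within 0.1 percentage point. The excess is never negative, so no true adult is placed in an adolescent group. The mean excess is 0.5 + f, or 0.5 to 0.8 years.

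**Illustrative dates.**
- Born 15 Dec 1998, consent 20 Jan 2016, first prophylaxis 20 Apr 2016: true age 17; formula 2016 − 1998 = 18 (EMA adult).
- Born 20 Dec 1998, consent 15 Nov 2015, first prophylaxis 15 Feb 2016: true age 16; formula 2016 − 1998 = 18, an excess of 2.
- Born 15 Dec 1999, consent 20 Jan 2016, first prophylaxis 20 Apr 2016: true age 16; formula 2016 − 1999 = 17 (FDA adult).

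**The case against.** The strongest reply is that the subgroup rule sits in 5.12, and 5.12 is already right. If the Demographics panel holds a recorded age at consent and the programmer reads it directly, nobody is misclassified and nobody in the safety population lacks an age. This stands as a limit on the consequence: the documents do not establish that the 6.2 formula feeds the groups. It does not remove the error, because 6.2 then gives a different value for the identically named variable.

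Three stronger inferences are tempting and not supported:
- *That subjects without an age vanish from the safety tables.* No rule excludes them. SAP 5.9 takes the relevant analysis set and arm as the default denominator and has a category for unavailable results, although it does not say how this works for a grouping variable. The adverse event, laboratory and vital-sign listings would still show these subjects.
- *That the models are affected.* The imputation model (SAP 5.5.1.1) and the negative binomial model (SAP 7.1.2) use age at baseline, a different label with no stated formula. It might inherit the 6.2 rule, but nothing says so. SAP 5.6 ties baseline to the reference start date, so an age anchored there may be intended. The ABR comparisons use prophylactically treated subjects, so missing age should not arise in them.
- *That one figure of about 8% describes the misclassification.* That is the zero-lag floor for the EMA cut-off only.

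**Conclusion.** The point holds as a minor but definite inconsistency. The 6.2 rule is wrong for the variable it names, and it contradicts 5.12. Its effect on the age groups is conditional on the formula being used to form them.

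Under that condition, safety subjects without a prophylactic dose cannot be placed in an age group, and between 50% (no lag) and 76% (112 days) of true 17-year-olds are counted as EMA adults, with 70-73% at the planned lag. These percentages rest on the uniformity assumptions. Transitioning subjects who skip the PK assessment may have a shorter lag. Sites granted screening exemptions (Protocol 10.3) may have a longer one. Neither the number of adolescents near the cut-offs nor the number of subjects treated without prophylaxis is given, so no count can be stated. The primary chi-square comparison contains no age term.

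**What to change.** Replace the formula in SAP 6.2 with the age at informed consent recorded on the Demographics eCRF, as 5.12 already states. If the panel holds a full birth date rather than an age, use completed years at the consent date. Use one label throughout, and use this variable for the EMA and FDA age groups.

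If only year of birth is collected, use year of informed consent minus year of birth. This gives every safety subject an age and removes the lag error. It does not remove the birthday error: under the same assumptions about 50% of true 17-year-olds would still be classed as adults, and the SAP should say so. The annotated study book cited in the SAP references should show which case applies; it is not among the documents reviewed.

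It would also help to say how age at baseline is derived for the models, since no definition is given. The cost is one line in the SAP and a check of the age derivation in the programming; no new data are needed if the panel holds an age or a birth date.

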8.5 Randomization and Blinding

This is a randomized, open-label, concurrent, dose regimen comparison clinical study. In order to minimize/avoid bias, once eligibility is confirmed, subjects will be randomly assigned to one of 2 treatment regimens with PK-guided dosing targeting FVIII trough levels of 1-3% or approximately 10% (8-12%) in a 1:1 ratio. Randomization occurs after the PK assessment and will be stratified according to subjects' pre-study treatment regimen/ABR (prophylaxis with ABR <5 vs. prophylaxis with ABR ≥5 vs. on-demand).

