13.6 Medical, Medication, and Non-Drug Therapy History

At screening, the subject's medical history will be described for the following body systems including severity (defined in Section 13.2.5) or surgery and start and end dates, if known: eyes, ears, nose, and throat; respiratory; cardiovascular; gastrointestinal; musculoskeletal; neurological; endocrine; hematopoietic/lymphatic; dermatological; and genitourinary.

The historical ABR including treated and untreated bleeding episodes in the 12 months prior to study enrollment based on medical records should also be recorded in the eCRF. Only the treated bleeds will be the basis for inclusion in the study.

All medications taken and non-drug therapies received from 4 weeks before enrollment until completion/termination will be recorded on the concomitant medications and non-drug therapies CRFs.

Any prior use of any pegylated medication (name of drug, indication, and dates of use), at any time in the past, will be recorded on the eCRF.

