2.4 Randomization and Blinding

This is a randomized, open-label, concurrent, dose regimen comparison clinical study. In order to minimize/avoid bias, once eligibility is confirmed, subjects are randomly assigned to one of two treatment regimens with PK-guided dosing targeting FVIII trough levels of 1-3% or approximately 10% (8-12%) in a 1:1 ratio. Randomization occurs after the PK assessment and is stratified according to subjects' pre-study treatment regimen/ABR (prophylaxis with ABR <5 vs. prophylaxis with ABR \geq 5 vs. on-demand).

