The analysis of this data involves the use of a multiple imputation technique on a transformation of this data. See Section 5.5: Handling of Missing, Unused, and Spurious Data. This is the primary analysis for the PROPEL study.

The primary analysis will be repeated as a sensitivity analysis with the following alternative imputations:

- Standard uninflated imputation (excluding regular post-PROPEL bleeds).
- Imputed bleeds with the mean inflated by 10%.
- Imputed bleeds with the mean inflated by 20%.
- Imputed bleeds with the mean inflated by 40%.
- Imputed bleeds with the mean inflated by 80%.
- Worst case bleed imputation (See Section 5.5: Handling of Missing, Unused, and Spurious Data).

The proportion of subjects with total ABR <2, spontaneous ABR <2, Spontaneous ABR = 0, spontaneous AJBR <2 and spontaneous AJBR = 0, for the second 6-month period (ObsDay 183 to ObsDay364) as well as the full 12-month period treatment period (ObsDay 1 to ObsDay 364), will be analyzed in the same manner as the primary efficacy outcome. The sensitivity analysis described above for the primary efficacy outcome, will not be applicable to the secondary efficacy outcomes.

The total ABR, injury related ABR, spontaneous ABR and spontaneous AJBR, will be analyzed using a generalized linear model fitting a negative binomial distribution with logarithmic link function for the second 6-month period (ObsDay 183 to ObsDay 364) as well as the full 12-month observation period (ObsDay 1 to ObsDay 364). Separate Negative Binomial models will be used for these two time periods. The model is to include the treatment arm assigned (low level or high level), Stratum and race as fixed effects, age at baseline as continuous covariate and the logarithm of the OPE in years as an offset. The following SAS[®] code can be used to perform the analysis:

```
Proc Genmod Data = <Dataset>;
```

```
Class <Treatment> <Strat> <Race> (param=ref ref=first);  
Model <Bleeds> = <Treatment> <PREABR> <Baseline_age> <Race> / type3  
dist = negbin link = log offset = <log_OPE>;  
lsmeans <treatment> / bylevel om CL;  
ODS OUTPUT LSMEANS = <Outdata>;  
Run;
```

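### The printed SAS code for the secondary ABR models omits the randomisation stratum, and separately the SAP 6.2 pre-study ABR grouping does not match the strata it says it follows

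*SAP*

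**What the plan says.** **The strata.** Protocol 8.5 randomises within "prophylaxis with ABR <5 vs. prophylaxis with ABR ≥5 vs. on-demand". SAP 2.4 repeats this: "Randomization occurs after the PK assessment and is stratified according to subjects' pre-study treatment regimen/ABR", with the same three levels. SAP 5.12 defines the analysis variable, "Stratum, as derived from the pre-study ABR and pre-study treatment type", again with prophylaxis below 5, prophylaxis 5 or more, and on-demand.

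**The secondary ABR models.** Protocol 14.4.2 lists study arm, stratum, age and race as covariates of the negative binomial model for the bleed rate. The prose of SAP 7.1.2 agrees: treatment arm, stratum and race as fixed effects, age as a continuous covariate, and log observation time as offset. The sample code that follows has `<Strat>` in its CLASS statement, and the legend explains it as the stratum category. The MODEL statement, however, reads "Model <Bleeds> = <Treatment> <PREABR> <Baseline_age> <Race> / type3".

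**The baseline grouping.** SAP 6.2 first gives a detailed list, "Average ABR based on previous twelve months will be categorized as", whose bins include 3 to <5 and 5 to <7. It then adds "A condensed categorization of ABR based on the previous twelve months, corresponding to the stratification of subject will be made as follows", followed by two groups, ≤5 and >5.

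**The concern.** Pre-study regimen and bleeding rate is the only factor on which allocation was stratified. A reader expects the models that compare bleeding rates to adjust for it, because both documents say they will, and expects any baseline table labelled as following the stratification to show those strata.

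The MODEL line puts the first expectation in doubt. If it is programmed as printed, the secondary treatment comparisons come from models that differ from the prespecified ones, and the difference would not be visible in the SAP prose. The SAP 6.2 labels fail the second expectation: counts by the condensed grouping would not reconcile with counts by stratum.

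**Working it through.** The plan gives no figure to reproduce on this point. The check sets the texts side by side.

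**1. The model code (SAP 7.1.2)**

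| Source | Term for the stratification factor |
|---|---|
| Protocol 14.4.2 | stratum |
| SAP 7.1.2, prose | stratum, fixed effect |
| SAP 7.1.2, CLASS line | `<Strat>` |
| SAP 7.1.2, legend | `<STRAT>`, the stratum category |
| SAP 7.1.2, MODEL line | `<PREABR>`; no `<Strat>` |
| SAP 5.5.1.1, imputation model | `<Stratn>`, in both CLASS and MODEL |

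- A variable named in CLASS but absent from MODEL is not fitted, so the printed code has no stratum term.
- `<PREABR>` is not explained in the legend. Because it is not in CLASS, a numeric variable of that name would enter as one continuous slope. That is not the three-level factor, and it carries no contrast between on-demand and prophylaxis.
- Models affected: total, injury-related and spontaneous ABR and spontaneous AJBR, each for the second six months and for twelve months, so 4 × 2 = 8.
- Not affected: the primary chi-square test, which has no covariates; the secondary proportions, which SAP 7.1.2 analyses in the same way as the primary outcome; and the imputation model, which uses the stratum correctly.

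**2. The baseline grouping (SAP 6.2)**

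Applying each rule to a prophylaxis subject:

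| Pre-study ABR | Randomisation and SAP 5.12 | SAP 6.2 condensed group | Same side? |
|---|---|---|---|
| 4 | <5 | ≤5 | yes |
| 4.9 | <5 | ≤5 | yes |
| 5 | ≥5 | ≤5 | **no** |
| 5.1 | ≥5 | >5 | yes |
| 6 | ≥5 | >5 | yes |

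- Only the value 5 changes side. It is attainable: Protocol 13.6 has sites record "The historical ABR including treated and untreated bleeding episodes in the 12 months prior to study enrollment based on medical records", which is a count over one year and so normally a whole number.
- On-demand subjects form their own stratum whatever their ABR. In SAP 6.2 they fall into either group with the prophylaxis subjects, so correcting the inequality signs alone would not restore the strata.
- The detailed bins in the same section place 5 in the upper bin (5 to <7). They collapse to <5 and ≥5 but cannot be collapsed to ≤5 and >5, so SAP 6.2 also disagrees with itself.
- Neither SAP 5.8 (changes from the protocol) nor the revision history mentions a new cut or a changed covariate.

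**3. Number of subjects at exactly 5**

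The documents do not give it. Purely as an assumption, if 2% to 10% of the 116 planned subjects were on prophylaxis with ABR exactly 5, then 0.02 × 116 = 2.3 and 0.10 × 116 = 11.6, or about 2 to 12 subjects with a mismatched label.

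**The case against.** The best defence of the code is that it is offered as an example. The prose, the CLASS line, the legend and SAP 5.12 all point to stratum, so a careful programmer would see the slip and correct it. That is fair as to intent, and it makes the error likely to be caught. It does not make the printed statement right: the one line that determines what is fitted contradicts the text around it, and an undefined name leaves the programmer to guess.

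The best defence of SAP 6.2 is that nothing inferential uses the grouping, and that the detailed bins let a reader recover the <5 and ≥5 split. Both points stand. The bins still do not separate regimens, so they do not recover the three strata.

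A reader might go further, in four ways that the documents do not support:

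- **That the mis-cut grouping enters the model through `<PREABR>`.** No text links the two. `<PREABR>` could equally mean the pre-study ABR itself. The two slips should be treated as separate.
- **That a sizeable share of the upper prophylaxis stratum is misallocated.** Assuming a pre-study mean of 4 to 8 bleeds, a negative binomial with variance equal to mean + k × mean² and k of 0.5 to 1 puts 11% to 25% of subjects with 5 or more bleeds at exactly 5. A Poisson with the same means gives about 10% to 42%. The spread shows how little anchors these figures, since the documents give no distribution. In any case nobody's randomisation stratum or SAP 5.12 stratum changes; only a descriptive label does.
- **That every subject with exactly 5 bleeds is on the wrong side.** This applies to prophylaxis subjects only, because on-demand subjects had no ABR cut at randomisation.
- **That the true strata will not be tabulated at all.** SAP 5.12 lists stratum as a subgroup to be used as the Output Templates indicate. Those templates are not among the documents, so this cannot be said either way.

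**Conclusion.** Both inconsistencies are certain from the text, and they differ in weight.

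The MODEL line is the more important. As printed, it drops the stratification factor from the eight secondary ABR models, contrary to the SAP prose and Protocol 14.4.2. The effect on the estimated rate ratios and their intervals cannot be calculated from the documents; it depends on what is programmed as `<PREABR>` and on how strongly stratum predicts bleeding. Because allocation was stratified, marked imbalance between arms on this factor is not expected, so the main issues are precision and departure from the prespecified model.

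The SAP 6.2 grouping is a labelling error in descriptive baseline tables. It misplaces prophylaxis subjects with ABR exactly 5, whose number is not given, and it merges the on-demand stratum into the other two.

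A reader might infer that the primary result is at risk. It is not: the primary test is unstratified, and the imputation behind it uses the correct stratum variable.

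**What to change.** 1. In the SAP 7.1.2 MODEL statement, replace `<PREABR>` by `<Strat>`, already in CLASS and defined in the legend, and state that it is the three-level variable of SAP 5.12. If a separate adjustment for pre-study ABR was intended as well, define it and list it in SAP 5.8 as a change from the protocol.
2. In SAP 6.2, replace ≤5 and >5 by the three strata of SAP 5.12 (prophylaxis <5, prophylaxis ≥5, on-demand), or refer to that section.

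The cost is two text edits and a check of the corresponding programs. No new data are needed, and the primary analysis does not change.
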